### 7.6.4. Handling of missing stop dates of prior and concomitant therapies

For therapies marked as “ongoing”: the stop date will not be imputed. For therapies marked as “not ongoing”, the stop date will be imputed as below.

|                           |   |
|---------------------------|---|
| Stop date of therapy      | Imputed stop date   |
| Completely missing        | No imputation. The therapy will be considered as “ongoing” for the analysis.  |
| Day is missing            | Last day of the month.

For therapy collected in the “D-15 / Hospitalisation” form: if imputed date is later than the end of hospitalisation visit date, then replace with the end of hospitalisation visit date.

For therapy collected in the “Follow-up” form: if imputed date is later than the date of last contact, then replace with the date of last contact. |
| Day and month are missing | 31 December

For therapy collected in the “D-15 / Hospitalisation” form: if imputed date is later than the end of hospitalisation visit date, then replace with the end of hospitalisation visit date.

For therapy collected in the “Follow-up” form: if imputed date is later than the date of last contact, then replace with the date of last contact.            |

Note: partially or completely missing start dates of therapies will not be imputed.

## 7.7. Other programming rules

Lost to follow-up patients at M3, M6, M12 and M18 will be computed as follows.

Lost to follow-up at M18:

- Yes, if 'lost-to-follow-up' is ticked 'yes' in End of Study form
- No, otherwise

Lost to follow-up at M12:

- Yes, if 'lost-to-follow-up' is ticked 'yes' in End of Study form
  - and visit M12 was not performed
  - and visit M18 was not performed
- No, otherwise

Lost to follow-up at M6:

- Yes, if 'lost-to-follow-up' is ticked 'yes' in End of Study form
  - and visit M6 was not performed
  - and visit M12 was not performed
  - and visit M18 was not performed
- No, otherwise

Lost to follow-up at M3:

- Yes, if 'lost-to-follow-up' is ticked 'yes' in End of Study form
  - and visit M3 was not performed
  - and visit M6 was not performed
  - and visit M12 was not performed
  - and visit M18 was not performed
- No, otherwise

Note: at the time of writing, no patient who ticked 'lost-to-follow-up' in End of Study form performed and unscheduled visit.

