## **8. Withdrawal Criteria**

### **8.1. Patient Withdrawal from the Study and Replacement of Patients**

A patient may be withdrawn from the study in the following cases:

- withdrawal of consent by the patient or his/her legal representative;
- study termination by the Sponsor.

If the patient withdraws his/her consent, no further study assessments will be performed and no further data will be collected, with the exception of safety data and data on the patient's clinical status, which must be collected whenever possible.

If a patient decides to withdraw from the study, the reason must be recorded in the CRF. If a patient is withdrawn from the study due to an AE, all necessary measures must be taken to clearly document the outcome of the AE.

Data collected prior to withdrawal of the patient will be taken into account in the PK, efficacy and safety analyses, except in the event of patient refusal.

Patients withdrawn from the study will not be replaced.

If a patient is lost to follow-up for reasons related to armed conflict or natural disaster, after several unsuccessful attempts have been made to contact him/her, and if no data are available after the treatment period, the patient will be removed from the primary analysis and another patient will be added in order to maintain the planned sample size, provided that the enrolment period is still on-going.

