## 9.8. Handling of Missing Data and Patients Lost to Follow-up

The primary endpoint is the outcome at 18 months. If outcome assessed at the final visit is missing, the **primary imputation method** will consist in imputing a probable success (considered as a success) to patients who attended the 18-month visit, but who refused the lumbar puncture planned at the visit, who showed no signs or symptoms of HAT at 18 months, who did not subsequently report any symptoms of relapse and for whom the outcome was considered as favourable at the last available assessment (17). If these criteria are not fulfilled, the patients will be considered as treatment failures. The outcome for patients who did not attend the 18-month visit or later will also be considered as a failure, except for patients who fled the region due to armed conflict or natural disaster.

Because the historical data may not allow for other imputation methods to be applied, only the primary imputation method will be used. The method will be described in detail in the SAP. Sensitivity analyses will be performed to assess the impact of missing data on acoziborole. The method will be described in detail in the SAP.

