## 6. DEFINITION OF ENDPOINTS

### 6.1. Primary efficacy endpoint

#### Primary endpoint for patients with Stage 2 HAT

The primary endpoint is the outcome (success or failure) at the 18 months visit according to the adapted WHO criteria:

- Success is defined as a cure or a probable cure (cf. algorithm in [Section 10.1](#)).
- Failure is defined as a relapse, probable relapse, death for any reason (up to and including the 18 months visit) or use of rescue medication (up to and including the 18 months visit) or lost to follow-up for any reason (up to and including the 18 months visit) or refusal of all post-treatment lumbar puncture (up to and including the 18 months visit) or had unfavourable outcome earlier than M18 or sign and symptoms evoking a relapse at M18 (cf. algorithm in [Section 10.1](#)).

Note: data review committee composed of those involved in the study conduct and data processing will check before database lock the status of patients (success or failure) using the algorithm presented in [Section 10.1](#).

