### 7.6.2. Handling of intercurrent events

The handling of post-treatment intercurrent events such as rescue medication intake, death, early consent withdrawal, lumbar puncture refusal, study discontinuation including war and natural disaster are taken into account in the algorithm for determining the outcome and in population definitions. Concomitant therapies other than rescue medication are not taken into account in the assessment of efficacy.

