## 10. KEY DERIVED VARIABLES

### 10.1. Outcome at 18 months

| Derivation algorithm for stage 1 and intermediate stage (month 18)   | Derivation algorithm for stage 2 (Month 18)  |
|--|--|
| 
Patient is → 1: Dead (any reason of death and any time between drug intake and M18) ⇒ Failure (stop)
         ↓
         Alive
         ↓
 Patient requires rescue medication for HAT at M18 or required it before (between drug intake and M18)
         → YES → 2: (definitive) Failure (stop)
         ↓
         NO rescue medication so far
         ↓
 Evidence of trypanosomes in any body fluid between drug intake and M18 visit ⇒ YES ⇒ 3: (definitive) Failure (stop)
         ↓
         NO observed trypanosomes
         ↓
 Patient Lost to follow-up at M18 (no survival information at M18 and later)
         → YES ⇒ 4: Failure (Stop) [a,b]
         ↓
         NO (the patient is not lost to follow-up)
         ↓
 Non-hemorrhagic lumbar puncture at M18 and WBC in CSF at M18 > 20 cells
         → YES ⇒ 5: Failure (stop)
         ↓
         NO (WBC in CSF at M18 ≤ 20 cells or no reliable data concerning WBC in CSF at M18)
         ↓
 Non-hemorrhagic lumbar puncture at M18 and WBC in CSF ≤ 20 cells
         → YES ⇒ 6: Success (stop)
         ↓
         NO (hemorrhagic CSF sample or no lumbar puncture at M18 for any reason)
         ↓
 No lumbar puncture at M18 or no reliable count of WBC in CSF at M18 but reliable number of WBC in CSF reported later (M24 or other additional visit)
         → YES ⇒ WBC in CSF > 20 ⇒ 7: Failure (Stop)
         → YES ⇒ WBC in CSF ≤ 20 ⇒ 8: Success (Stop)
         ↓
         NO (No lumbar puncture at M18 and no later reliable count of WBC in CSF)
 | 
Patient is → 1: Dead (any reason of death and any time between drug intake and M18) ⇒ Failure (stop)
         ↓
         Alive
         ↓
 Patient requires rescue medication for HAT at M18 or required it before (between drug intake and M18)
         → YES ⇒ 2: (definitive) Failure (stop)
         ↓
         NO rescue medication so far
         ↓
 Evidence of trypanosomes in any body fluid between drug intake and M18 visit ⇒ YES ⇒ 3: (definitive) Failure (stop)
         ↓
         NO observed trypanosomes
         ↓
 Patient Lost to follow-up at M18 (no survival information at M18 and later)
         → YES ⇒ 4: Failure (Stop) [a,b]
         ↓
         NO (The patient is not lost to follow-up)
         ↓
 Non-hemorrhagic lumbar puncture at M18 and WBC in CSF at M18 > 20 cells
         → YES ⇒ 5: Failure (stop)
         ↓
         NO (WBC in CSF at M18 ≤ 20 cells or no reliable data concerning WBC in CSF at M18)
         ↓
 Non-hemorrhagic lumbar puncture at M18 and WBC in CSF ≤ 20 cells
         → YES ⇒ 6: Success (stop)
         ↓
         NO (hemorrhagic CSF sample or no lumbar puncture at M18 for any reason)
         ↓
 No lumbar puncture at M18 or no reliable count of WBC in CSF at M18 but reliable number of WBC in CSF reported later (M24 or other additional visit)
         → YES ⇒ WBC in CSF > 20 ⇒ 7: Failure (Stop)
         → YES ⇒ WBC in CSF ≤ 20 ⇒ 8: Success (Stop)
         ↓
         NO (No lumbar puncture at M18 and no later reliable count of WBC in CSF)
 |

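### The SAP does not require attendance at month 18 for a stage 2 success, so a patient not seen at month 18 or later can be counted as cured, contrary to Protocol 9.8

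*SAP*

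**What the plan says.** **Protocol 9.8** imputes a probable success only to "patients who attended the 18-month visit, but who refused the lumbar puncture planned at the visit", provided there are also no signs of disease and the last available outcome was favourable. It then adds: "The outcome for patients who did not attend the 18-month visit or later will also be considered as a failure". The exception is patients who fled armed conflict or natural disaster.

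**The SAP** describes loss to follow-up at month 18 in three ways:

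- Section 7.7 uses the End of Study form alone: "Yes, if 'lost-to-follow-up' is ticked 'yes' in End of Study form", otherwise no. The rules for months 12, 6 and 3 in the same section also require visits not to have been performed; the month-18 rule does not.
- Section 10.1, at step 4 (the numbered outcomes of the table are called steps here), explains it as "no survival information at M18 and later".
- Section 6.1 counts as failure "lost to follow-up for any reason (up to and including the 18 months visit").

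SAP 8.1 records withdrawal of consent, investigator's decision and other reason separately from loss to follow-up. SAP 7.6.2 states that "early consent withdrawal, lumbar puncture refusal, study discontinuation including war and natural disaster are taken into account in the algorithm" and in the population definitions. No stage 2 month-18 step names withdrawal or discontinuation. SAP section 11 declares changes to adverse-event counting, stage wording and the yardstick, but none to Protocol 9.8.

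**The concern.** Steps 5 and 6 of SAP 10.1 need a lumbar puncture at month 18. Steps 7 and 8 need a later cell count, which fits the protocol's allowance for later visits. The gap is in the fallback route through steps 9 to 11.

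A patient who leaves after month 6 or 12 can pass step 4 in two ways. Either the form gives an exit reason other than loss to follow-up (section 7.7), or the patient is known to be alive but is not seen (the wording of step 4). The second is realistic, because Protocol 8.1 stops data collection after withdrawal of consent "with the exception of safety data and data on the patient's clinical status, which must be collected whenever possible".

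Step 11 then grants success on acceptable earlier cell counts plus absence of signs at month 18, without saying that the signs must have been assessed. The negative branch of step 9 expressly admits missing information; that of step 10 says nothing about it. Nor does the SAP say whether a status report without a visit counts as a month-18 assessment of signs.

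The primary outcome of one and the same patient therefore turns on a reading left to the programmer. One reading favours the drug and contradicts the protocol. There is no formal success rule, and the observed rate and its lower bound are what will be interpreted, so a few patients can matter.

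**Working it through.** **1. The plan's own precision.** The Jeffreys interval runs from the 2.5% to the 97.5% quantile of Beta(x + 0.5, n − x + 0.5), with n = 155 (Protocol 9.1).

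- 138/155 = 89.0%: 83.4 to 93.2, as stated.
- 146/155 = 94.2%: 89.7 to 97.1, as stated.

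**2. Four patients through the stage 2 month-18 steps.** All are alive, without rescue treatment or trypanosomes, with CSF white cells of 15 at month 6 and 8 at month 12, and no later puncture.

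| Patient | Loss rule | Unobserved signs read as absent | Read as criterion not met | Protocol 9.8 |
|---|---|---|---|---|
| Withdrew, not ticked as lost, no month-18 information | 7.7 | step 11 success | step 13 failure | failure |
| | step 4 wording | step 4 failure | step 4 failure | |
| Known alive, no visit, not ticked | 7.7 or step 4 wording | step 11 success | step 13 failure | failure |
| Ticked as lost, but known alive | 7.7 | step 4 failure | step 4 failure | failure |
| | step 4 wording | step 11 success | step 13 failure | |
| Attended, refused puncture, no signs | either | step 11 success | step 11 success | success |

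**3. Sixteen combinations.** Month-6 count none, 15, 35 or 60, crossed with month-12 count none, 10, 18 or 30, for a patient not seen at month 18 or later.

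- Not ticked (7.7), signs read as absent: 5 of 16 are step 11 successes (15/none, 15/10, 35/none, 35/10, 35/18).
- Known alive (step 4 wording), signs read as absent: the same 5.
- Signs read as criterion not met: 0 of 16.
- Ticked as lost under 7.7: 0 of 16.

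The 35/none patient is a failure at month 6 (step 7 of SAP 10.3) and at month 12 (step 12 of SAP 10.2), yet a success at month 18.

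**4. Sensitivity analyses, signs-absent reading.** None of the primary and six sensitivity analyses counts these patients as failures throughout. They are successes in the mITT, Treated and best-case analyses; in the Evaluable set, which removes consent withdrawals only before month 6; and in the per-protocol set if there is no major deviation. They are resampled in fair case and missing in observed case.

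**5. Size.** Each patient moves the rate by 1/155 = 0.65 points. The number affected is not in the documents. For scale only, SAP 8.6.1.3 reports that in the 2009 randomised NECT trial of 143 patients, 2 moved out and 4 lacked a month-18 assessment. Scaled by 155/143, 2, 4 and 6 patients become 2.2, 4.3 and 6.5. Recoding 0, 2, 4 or 6 of 155 to failure gives:

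| Starting point | 0 | 2 | 4 | 6 |
|---|---|---|---|---|
| 151/155 (assumed) | 97.4% (94.0–99.1) | 96.1% (92.2–98.4) | 94.8% (90.5–97.5) | 93.5% (88.9–96.6) |
| 146/155 | 94.2% (89.7–97.1) | 92.9% (88.1–96.2) | 91.6% (86.5–95.2) | 90.3% (84.9–94.2) |
| 138/155 | 89.0% (83.4–93.2) | 87.7% (81.9–92.2) | 86.5% (80.4–91.2) | 85.2% (78.9–90.1) |

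With 6 recoded, the lower bound falls by 5.1, 4.8 and 4.5 points respectively.

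**The case against.** The strongest reply is that the text leans towards failure. Step 11 requires absence of signs at month 18, its exit covers any criterion not met, and step 13 sends everything else to failure. Where the SAP lets missing information pass, it says so, as in step 9; steps 10 and 11 contain no such allowance for signs. Step 4 also carries its own definition and does not cite section 7.7, so a withdrawn patient with no later information may already fail there. This is a fair reading, and on it the primary analysis matches Protocol 9.8. But it is not written down, and section 7.7 gives an explicit programming rule for the same variable that points the other way.

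Protocol 2.2.1 classes a patient who refuses the final puncture as a probable cure without expressly requiring attendance, and Protocol 8.1 keeps data collected before withdrawal in the efficacy analysis. Neither displaces the explicit rule for non-attenders in 9.8.

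The NECT counts are not shown to be the affected kind of patient: the 2 who moved would fail at step 4 if ticked as lost, and the 4 may have attended and refused puncture. That stands, so they serve only as a scale.

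Safeguards exist. Disposition tables will show attendance and exit reasons, the primary endpoint is double-programmed, and a "data review committee composed of those involved in the study conduct and data processing will check before database lock the status of patients". The committee and the second programmer work from the same algorithm, so they may expose a divergence but cannot supply the missing rule.

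**Conclusion.** The concern holds and should be fixed. The SAP words month-18 loss to follow-up inconsistently, leaves attendance out of the route to success at step 11, and declares no departure from Protocol 9.8. The wrong classification is conditional: it needs unobserved signs to be read as absent, and a patient who passes step 4 through the unticked form or through being known alive. The effect is 0.65 points per patient, in the drug's favour. The total is unknown and may be zero; the fall of 0 to about 5 points in the lower bound rests on an assumed 0 to 6 patients among 155.

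**What to change.** In SAP 10.1 (month 18):

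- Add a step after step 8 and before step 11: a patient with no visit at month 18 or later, whatever the exit reason, is a failure. Make step 11 conditional on signs and symptoms having been assessed at such a visit.
- Leave the 7.7 variable as it is, so that membership of the Evaluable set does not change, and state that it does not by itself decide step 4.
- Keep the Protocol 9.8 exception for patients who fled conflict or disaster. Reconcile it with the SAP mITT definition, which removes them only if they have no data at months 12 and 18 and no early failure.
- State the sensitivity handling. Marking the new step [a,b] like step 4 gives success in best case and resampling in fair case, as step 11 does now on the signs-absent reading.
- State whether the new failure carries back to step 10 at month 12 and step 7 at month 6, and exclude it there if that is not intended. Protocol 2.2.2 uses the 6-month outcome at month 12 when there is no later puncture and the patient is not lost to follow-up, so for a month-6 count of 20 or below carry-over would not match it.

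A phrase in step 11 alone would settle the primary analysis through step 13, but step 13 carries no sensitivity mark, so those decisions would still be needed. The signs-absent classification can be kept as a sensitivity analysis.

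The cost is SAP wording, one derived variable from visit dates already collected, and a possibly slightly lower success rate. If carry-over is not excluded, month-12 outcomes change in 1 of the 5 paths (15/none) and month-6 outcomes in 2 (35/10 and 35/18). This takes a month-12 count of 20 or below as a month-12 success, because no step 7 is visible in the stage 2 column of SAP 10.2.

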## 8. PLANNED STATISTICAL ANALYSES

### 8.1. Disposition of patients

Disposition of patients and reasons for premature discontinuations of follow-up will be tabulated by cohort (i.e. separating stage 2 patients from stage 1 and intermediate-stage patients), by stage of disease and overall.

- Number of screened HAT positive patients (i.e. patients who gave informed consent)
  - Number and percentage of patients who met all inclusion criteria and no exclusion criteria
  - Number and percentage of patients with at least one inclusion criterion not met and/or exclusion criterion met
- Number of patients not treated, and reasons:
  - Number and percentage of patients with at least one inclusion criterion not met and/or exclusion criterion met
  - Number and percentage of patients not treated due to SAE not related to treatment
  - Number and percentage of patients not treated due to early consent withdrawal or another reason (will be listed)
- Number of patients treated (i.e. who received at least one of the 3 tablets of acoziborole)
- Amongst treated patients:
  - Number and percentage of patients who withdrew from the study prematurely, listed by reason for withdrawal (i.e. death, lost to follow-up, withdrawal of consent, investigator's decision, rescue therapy, other reason)
  - Number and percentage of patients who completed the trial according to the protocol
- The following data will also be provided amongst treated patients:
  - Number and percentage of patients who fled the region due to armed conflict or natural disaster or due to force majeure and for whom no post-treatment data are available (i.e. follow-up visits M3, M6, M12 and M18 not performed).
  - Number and percentage of patients who died for reasons clearly unrelated to the IP or HAT
  - Number and percentage of patients who had at least one minor protocol deviation
  - Number and percentage of patients who had at least one major protocol deviation (an intercurrent post treatment event is not necessarily a major protocol deviation)
  - Number and percentage of patients who underwent lumbar puncture at the end-of-hospitalisation, at the 6-month visit, the 12-month visit and the 18-month visit
  - Number and percentage of patients who attended the end-of-hospitalisation visit, the 3 months visit, the 6-month visit, the 12-month visit and the 18-month visit

In addition, the following data will be provided:

- Date of first patient screened
- Date of first administration of the first patient
- Date of first administration of the last patient
- Date of last patient last visit (i.e. last visit performed)
- Study duration (days) = date of last patient last visit - date of first administration of the first patient

## 8.2. Protocol deviations

Minor and major protocol deviations will be described separately. Results will be displayed by cohort, by stage of disease and overall, on the mITT.

Protocol deviations will be listed and finalised prior to the data review meeting. The sponsor will be responsible for classifying all deviations as either major or minor. Patients with at least one major protocol deviation will be excluded from the PP dataset. Major protocol deviations will be reviewed during the data review meeting.

## 8.3. Analysis sets and subgroups

Frequency and percentage of patients included in each analysis sets defined in [Section 5](#) will be provided, by cohort, by stage of disease and overall.

Frequency and percentage of patients included in each cohort, in each stage of the disease, and in each subgroup defined in [Section 5](#) will be described on the mITT.

## 8.4. Demographic data and baseline characteristics, including medical history, prior and concomitant therapies

Descriptive analyses will be provided by cohort, by stage of disease and overall, on the mITT set.

Medical and surgical history will be analyzed by MedDRA SOC and PT. Medical and surgical history will be tabulated with number of medical histories, number and percentage of patients with at least one medical history classified by SOC and preferred name.

Prior therapies and concomitant treatments will be tabulated with number of treatments, number and percentage of patients with at least one treatment classified by therapeutic class (ATC2) and preferred name.

## 8.5. Treatment compliance

Descriptive analyses will be provided by cohort, by stage of disease and overall, on the mITT set.

